6 PROCEDURES

Subjects will be screened for protocol eligibility during a period of no more than 28 days prior to enrollment in IVRS to receive induction therapy (the Screening period) as outlined in the Schedule of Study Assessments. Procedures conducted as standard of care may be used to meet the requirements of this study provided they meet the description and timeline specified in the protocol.

Cycle definition: defined in this study as lenalidomide Cycle; 21 days treatment + 7 days rest period = 28 days total.

6.1 Study Entry

6.1.1 Informed Consent Document

The subject must approve and sign the ICD prior to undergoing any study-related Screening assessments

6.1.2 Inclusion and Exclusion Criteria

The subject's eligibility (inclusion and exclusion criteria) must be evaluated during the Screening Period prior to enrollment in IVRS to receive induction therapy (see Section 7.2 and 7.3).

6.1.3 Demographic Data

The demographic data will include (but not be limited to) the subject's initials, date of birth, age, gender, and race/ethnic origin. The demographic profile will be recorded in the source documents and case report form (CRF).

6.1.4 Lymphoma and Complete Medical History

A medical history will be obtained by the investigator or qualified designee within 4 weeks prior to the first day of treatment. Medical history judged as relevant to the study and to the safety of the study subject will be recorded in the source documents and CRF.

Eligibility for FL grades 1-3b, transformed FL, MZL and MCL subjects will be based on local pathology review. For MCL confirmation of Cyclin D1 expression or the presence of the t(11;14) translocation is recommended. Diagnosis based on core biopsy is acceptable, but diagnosis based on fine needle aspiration is not considered acceptable pathologic data for entry into this study.

6.1.5 Bone Marrow Biopsy

Bone marrow biopsy is required at Screening (for staging). A recent bone marrow biopsy conducted within 24 weeks of Cycle 1 Day 1, is acceptable as the Screening biopsy. If no such recent bone marrow biopsy is available, then a repeat biopsy will be required prior to enrollment in IVRS to receive induction therapy. During the treatment period (induction or maintenance) of the study, a bone marrow biopsy is required only if the subject had positive bone marrow at Screening and has otherwise fulfilled the criteria for a nodal CR. The bone marrow procedure should be performed within 28 days after the criteria for radiological CR have otherwise been met. The biopsy may be unilateral or bilateral at the discretion of the investigator.

6.1.6 Endoscopy and Gastric Biopsy

Subjects with MZL involving the gastric area will undergo endoscopy as part of the response assessment. Histological evaluation for subjects with MZL involving the gastric area (for staging) based on endoscopy and gastric biopsy (from stomach, duodenum, and gastroesophageal junction and from any abnormal-appearing site) is required during Screening. A recent histological evaluation, conducted within 12 weeks prior to C1D1, is acceptable as the Screening assessment. If no such recent evaluation is available, then gastric repeat biopsy and histological evaluation will be required for subjects with MZL involving the gastric area prior to enrollment in IVRS to receive induction therapy.

Subjects with MZL involving the gastric area will have a repeat gastric biopsy for histological evaluation if the subject has fulfilled the IWG criteria for response of at least a CR/CRu. For subjects achieving radiological CR/CRu, a biopsy performed at two separate time points within 3 months after the criteria for CR/CRu were first met is required to confirm response. Histological evaluation of the gastric biopsy will be performed by the local pathologist. The Groupe d' Etude des Lymphomes de l' Adulte (GELA) grading system (Copie-Bergman, 2003; Copie-Bergman, 2012) is suggested to be used in the pathologic assessment.

6.1.7 Central Nervous System Lymphoma

Subjects with current or past Central Nervous System (CNS) lymphoma involvement are excluded from the study. Subjects with suspicion of CNS involvement must undergo neurologic evaluation and CT or MRI of brain and a lumbar puncture to exclude active CNS disease.

6.1.8 Lenalidomide Dosing - Creatinine Clearance (Cockcroft-Gault Estimation)

To determine the dose of lenalidomide on C1D1, the Cockcroft-Gault estimation of creatinine clearance (CrCl) will be assessed at Screening by the local laboratory utilizing actual body weight (Cockcroft, 1976; Luke, 1990; Griggs, 2012) and will be recorded in the source documents and CRF. See also Section 6.2.10.

CrCl (mL/min) = (140 - age) (weight [kg]) / 72 (serum creatinine [mg/dL]); for females, the formula is multiplied by 0.85.

6.1.9 12-Lead Electrocardiogram

12-lead electrocardiogram (ECG) is performed at Screening and as clinically indicated thereafter.

6.1.10 Hepatitis B

Hepatitis B Screening is required for all subjects and includes hepatitis B surface antigen (HBsAg), hepatitis B core antibody (anti-HBc) and hepatitis B surface antibody (anti-HBs). See exclusion criterion # 6 (Section 7.3) for further details. Eligibility for the study is based on the local HBV tests including if performed as standard of care within 4 weeks prior to enrollment in IVRS to receive induction therapy.

6.2 Safety Assessments

Serial assessments of safety will be performed as outlined in the Schedule of Study Assessments (Table 1).

Time to histological transformation will be measured based on documentation of histological transformation as assessed by the investigator. The date of the histology/pathology report will be used as the date of transformation. In case of clinical suspicion of transformation, including rapid disease progression, unexpected changes in "B" symptoms or rapidly increasing lactate dehydrogenase (LDH), a biopsy should be performed. In this clinical trial, histological transformation will be considered disease progression.

Subjects who relapse or progress will continue to be followed for SPMs for 5 years from the date of the last subject initiates induction therapy.

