Since the study endpoint is PFS based on CT, progression will typically be based on CT scans. In limited instances where progression is evident only by assessments other than CT, CT scans must still be provided along with the non-CT documentation of progression.

The radiological assessments (CT or MRI) and other assessments will be made according to a modification of the IWG 1999 criteria (Cheson, 1999), which are considered the primary method of response assessment. Scan results will be assessed by the Investigator or qualified site personnel. The modifications to the Cheson 1999 criteria are:

- Allow the inclusion of extranodal disease as measurable disease, as long as they fulfill all other requirements of measurable disease, including >1.5 cm in the longest transverse diameter.
- >2.0 cm bone marrow biopsy length is not required if the biopsy sample is considered adequate for assessment by the investigator.
- Gastric MALT subjects are required to undergo an additional evaluation of endoscopy and gastric biopsy at 2 time points within 3 months of radiologic evaluation demonstrating CR/CRu.
- PET scan is not considered part of the response criteria.

A similar modification to include extranodal disease as a measurable disease has been used previously (Fisher, 2006; Kane, 2007). The additional assessments – clinical assessments, bone marrow biopsy assessments, and endoscopic assessments (including biopsy) – are considered confirmatory to the initial CT scan findings. Bone marrow assessments are considered in the response assessment only in subjects with bone marrow involvement in the baseline bone marrow biopsy. Endoscopic biopsy and evaluation of the biopsy findings are required for confirmation of response only in subjects with an investigator-assessed pathologic diagnosis of MZL involving the gastric area. In those subjects whose CT/MRI response assessments require consideration of biopsy findings before a final response assessment can be determined, the date of achievement of a response status will be the initial date of CT or MRI showing a response.

Subjects who relapse or progress will continue to be followed for TTNLT and survival for 5 years from the date of the last subject initiating induction therapy.

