10.6.1 Primary Efficacy Endpoint

Progression-free Survival

The primary efficacy endpoint for the study is PFS, which is defined as the time from the first dose date of maintenance therapy to objective disease progression or death from any cause, whichever occurs first. The PFS events will be determined using a modification of the IWG 1999 criteria (Cheson, 1999).

Subjects who did not experience disease progression and who did not die before the clinical data cut-off date will be censored at the time of the last visit with adequate response assessment when the subjects were known not to have progressed. Subjects who received new anticancer therapy without objective disease progression will be censored at the date of the last radiological assessment prior to the new anticancer therapy.

The primary efficacy endpoint will be compared between the two treatment arms when 114 PFS events that happen after the first dose date of maintenance therapy are observed.

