Duration of response is defined only for subjects who have achieved PR or better after the first dose date of maintenance therapy and prior to any treatment change. It is calculated as the time from the initial response (at least PR) after the first dose date of maintenance therapy and prior to treatment change to documented disease progression or death.

Subjects who have not progressed or died at the time of the clinical data cutoff date will be censored at the last assessment showing no progression. Subjects who change treatment without evidence of disease progression will be censored at the last assessment showing no progression prior to treatment change.

Duration of Complete Response

Duration of complete response is defined only for subjects who have achieved CR/CRu after the first dose date of maintenance therapy and prior to any treatment change. It is calculated as the

time from the initial response (at least CRu) after the first dose date of maintenance therapy and prior to treatment change to documented disease progression or death.

Subjects who have not progressed or died at the time of the clinical data cutoff date will be censored at the last assessment showing no progression. Subjects who change treatment without evidence of disease progression will be censored at the last assessment showing no progression prior to treatment change.

Time to Next Anti-lymphoma Treatment

Time to next anti-lymphoma treatment is defined as the time from the first dose date of maintenance therapy to the time of first documented administration of new anti-lymphoma therapy. Subjects without new treatment therapy will be censored at the last visit.

Time to Histological Transformation

Time to histological transformation is defined as the time from the first dose date of maintenance therapy to the time of histological transformation as measured based on documentation of histological transformation (as assessed by the investigator). In case of clinical suspicion of transformation, including rapid disease progression, unexpected changes in "B" symptoms or rapidly increasing LDH, a biopsy should be performed. In this clinical trial, histological transformation will be considered disease progression. This endpoint will not be calculated for subjects randomized with transformed Follicular Lymphoma (tFL).

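### Histological transformation is dated by the pathology report, which lengthens TTHT by the reporting lag and leaves open whether a biopsy pending when new therapy starts is a PFS event or a censored observation (minor)

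*Combined protocol and SAP*

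**What the plan says.** Four parts of the combined protocol and SAP bear on this.

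- **Date of transformation (Section 6.2).** Directly after the sentence saying how TTHT is measured: "The date of the histology/pathology report will be used as the date of transformation". No section gives the biopsy date any role.
- **Status of transformation (Sections 6.2 and 10.6.2).** "In this clinical trial, histological transformation will be considered disease progression". Section 10.6.2 defines the endpoint: "Time to histological transformation is defined as the time from the first dose date of maintenance therapy to the time of histological transformation". It adds no date rule of its own. Biopsy follows clinical suspicion, such as rapid progression, changed B symptoms or "rapidly increasing LDH, a biopsy should be performed".
- **PFS (Section 10.6.1).** PFS is "the time from the first dose date of maintenance therapy to objective disease progression or death from any cause, whichever occurs first". Subjects who "received new anticancer therapy without objective disease progression will be censored at the date of the last radiological assessment" before that therapy form the censored group. Section 10.6.2 has a parallel rule for DOR and DOCR when treatment changes without evidence of progression.
- **Scans and response dates (Section 6.3).** Subjects who start new anti-lymphoma therapy without PD or relapse have no further radiological assessment. Where a response needs biopsy findings before it is final, "the date of achievement of a response status will be the initial date of CT or MRI showing a response".

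**The concern.** The report date measures laboratory and reporting time. It does not say when the transformed tissue was present. For TTHT this adds the lag to each event time.

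For PFS the matter is event status. Biopsy is prompted by signs of rapid change, and treatment may then begin before a formal report is issued. If it does, the only date the plan offers for that progression falls after new therapy starts. Section 10.6.1 does not say whether the absence of objective progression is judged at the start of new therapy or on everything known later. Two programmers could code the same subject differently.

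A subject coded as censored is removed for a reason tied to failure, so the censoring is informative. The censoring date goes back to the last scan, and scans are 168 days (±2 weeks) apart for most of follow-up.

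**Working it through.** **1. Order of dates.** Let M be the first maintenance dose, B tissue collection, N the start of new therapy and R the pathology report.

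TTHT under the plan is R − M. TTHT to tissue is B − M. The difference is R − B, the reporting lag, in every case.

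For PFS, take a subject with no earlier CT progression:

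| Order | PFS under the plan | PFS with tissue dating |
|---|---|---|
| R on or before N, or no N | event at R | event at B |
| N before B | not settled by the report-date rule | not changed by the fix |
| B on or before N, N before R; progression judged at N | censored at last scan before N | event at B |
| B on or before N, N before R; progression judged on all data | event at R, after N | event at B |

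A subject with CT progression before N is already an event on the CT date. Only the third row loses an event.

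**2. The plan's own figures.** Section 10.3 gives HR 0.533 as 20% better than assumed, so the assumed HR is 0.533/0.8 = 0.666. With Schoenfeld's formula, one-sided alpha 0.025 and 1:1 allocation:

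- Events for 80% power: 4 × (1.960 + 0.842)² / (ln 0.666)² gives 191. The plan states 191.
- Power at 114 events: Φ(√114/2 × |ln HR| − 1.960) gives 58.2%. The plan states 57.9%.
- Power at 114 events and HR 0.533: 91.9%. The plan states 92%.

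**3. How many subjects could be exposed.** The documents give neither the lag nor the count, so this is a range under assumptions.

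- From the documents: about 314 projected randomised and about 10% MCL (Section 10.3); FL transformation at about 2% to 3% per year (Section 1.1).
- Assumed: the FL rate applied to all non-MCL subjects, 2 to 4 years of follow-up, and 5% to 20% of transformations with new therapy between biopsy and report.

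Low end: 314 × 0.9 × 0.02 × 2 = 11.3 transformations; × 0.05 = 0.6.

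High end: 314 × 0.9 × 0.03 × 4 = 33.9 transformations; × 0.20 = 6.8.

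That is about 1 to 7 subjects before removing those with CT progression already recorded, so the range leans high.

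**4. Effect on power.** The analysis waits for 114 events, so a lost event mainly delays it. If events were lost outright at a fixed cut-off, power at HR 0.666 would be:

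| Events lost | Events left | Power |
|---|---|---|
| 0 | 114 | 58.2% |
| 1 | 113 | 57.9% |
| 5 | 109 | 56.4% |
| 8 | 106 | 55.2% |

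**5. Effect on the TTHT hazard ratio.** A simulation used 157 subjects per arm, a control rate of 3% per year, a true HR of 0.667 and 400 replicates. The median estimate was 0.66 with no lag. With equal mean lags of 7, 14 or 28 days (assumed) in both arms it was 0.65 to 0.66.

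**The case against.** The report-date sentence follows a sentence about TTHT and can be read as a TTHT rule only. Nothing says that it also dates the PFS event. Section 10.6.1 does not require progression to be dated before new therapy. Since transformation is progression, a subject with proven transformation can be read as having progressed, and so as an event. The route is also narrow: Section 6.3 expects progression to be shown typically on CT, and new or enlarging sites are already PD in Appendix E. Nothing in the documents shows that treatment starts before the report. The convention is prespecified and the same in both arms.

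Most of this stands. It makes the PFS loss conditional on four things together: no earlier CT progression, new therapy between biopsy and report, the report date carried over to PFS, and progression judged at the start of therapy. It does not remove the ambiguity, because no other date is supplied and no exception covers a pending biopsy.

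The contrast with response dating in Section 6.3 is suggestive only. There the CT has already shown the response and the biopsy confirms it, whereas transformation is itself a histological diagnosis.

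A reader might infer that the plan censors biopsy-proven transformations as a rule, or might set the 11 to 34 transformations above against 114 events and conclude that a large share of the primary endpoint is at risk. The documents support neither. Section 10.6.1 is open on the point, and the count includes transformations already captured by CT. It also applies a general FL rate to subjects selected for SD or better after 12 induction cycles.

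**Conclusion.** The point holds as a minor fault of definition. TTHT is lengthened by the reporting lag in every case. With lags that are short and similar between arms (assumed), absolute times shift slightly and the comparison hardly changes.

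For PFS, and likewise for DOR and DOCR when transformation is the first evidence of progression, event status can depend on laboratory turnaround under one admissible reading. The number affected cannot be derived from the documents. The range of about 1 to 7 rests on assumed follow-up, an assumed share treated before the report and no deduction for earlier CT progression, so a handful at most is likely. The harm is possible misclassification and informative censoring of those few subjects. The new-therapy censoring rule does the censoring; the dating rule helps decide who falls under it. The effect on power is negligible.

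**What to change.** In Sections 6.2, 10.6.1 and 10.6.2, date histological transformation at collection of the diagnostic tissue. Apply this date to TTHT, and to PFS, DOR and DOCR when transformation is the first evidence of progression. Add to Section 10.6.1 that tissue collected on or before the first day of new therapy, and later confirmed as transformation, is a PFS event on the collection date even if the report comes later.

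This changes an analysis definition only; treatment, visits and sample size stay as they are. The cost is a few sentences and one data item: the tissue collection date must be captured, and the documents do not say that it is. Affected event dates move slightly earlier.

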6.2.1 Adverse Events

Adverse events will be assessed and hospitalizations recorded from the signing of the informed consent form up to 28 days after the last dose of treatment with the exception of Second Primary Malignancies, see Section 6.2.2 below.

6.2.2 Second Primary Malignancies

Second primary malignancies are new cancers that are diagnosed in patients following a prior diagnosis of a first cancer. For the MAGNIFY trial, the primary (first) cancer is follicular grades 1-3b, transformed FL, marginal zone, or mantle cell lymphoma. Second primary malignancies will be monitored as events of interest and should be included as part of the assessment of adverse events throughout the course of the study. Investigators are to report any second primary malignancies as serious adverse events regardless of causal relationship to IP (study drug), occurring at any time for the duration of the study, from the time of signing the ICD for 5 years from the date the last subject initiates induction therapy.

6.2.3 Birth Control and Lenalidomide Counseling

Counseling about pregnancy precautions and the potential risks of fetal exposure must be conducted. During counseling, subjects must be reminded to not share study drug and to not donate blood. For all females of childbearing potential (FCBP)¹ two pregnancy tests must be performed prior to the first dose of study drug: one test during Screening period (10 to 14 days prior to the first dose of lenalidomide) and one test within 24 hours prior to the first dose of lenalidomide. See the Pregnancy Prevention Plan for more details (standalone document).

Counseling about pregnancy precautions and the potential risks of fetal exposure must be conducted on Day 1 of every lenalidomide treatment Cycle. All subjects must also be counseled against sharing lenalidomide and donating blood during and within 28 days of discontinuing

¹ Female of child-bearing potential definition: a female who: 1) has achieved menarche at some point, 2) has not undergone a hysterectomy or bilateral oophorectomy or 3) has not been naturally postmenopausal (amenorrhea following cancer therapy does not rule out childbearing potential) for at least 24 consecutive months (ie, has had menses at any time in the preceding 24 consecutive months).

protocol-specified therapy. Pregnancy tests for all FCBP will be performed weekly during the first Cycle, every 28 days (Day 1 of every Cycle) during treatment, at study discontinuation, and at Day 28 following study drug discontinuation. Additionally, for FCBP with irregular menstrual cycles pregnancy tests will be conducted weekly during the first 4 weeks of treatment and then every 14 days through 28 days following the last dose of lenalidomide. See the Pregnancy Prevention Plan for more details.

6.2.4 Study Drug Return/Accountability

The reconciliation of capsules will be done at the beginning of each Cycle and at treatment discontinuation. See Sections 8.4, 8.5, and 8.6 for more details.

6.2.5 Prior and Concomitant Medications, Procedures and Hospitalizations

Relevant prior and concomitant medications, procedures and hospitalizations will be collected from signing of informed consent through 28 days after the last dose of investigational product, and will be recorded in the source documents.

6.2.6 *Physical Examination*

The subject must have a physical examination performed within 4 weeks prior to the first day of treatment. The physical examination assessments should be repeated at the beginning of each Cycle, at treatment discontinuation and at any additional times as deemed necessary by the investigator. Investigators are required to report any clinically significant abnormal findings as AEs.

